LIST OF TABLES

Table 1. Schedule of Study Procedures and Assessments	15
Table 2. Frequency of measures and who completes each measure.....	21
Table 3. Dose Escalation Plan*.....	23
Table 4. Distribution of CGI-I for Secondary Efficacy Outcome Measure	34
Table 5. Distribution of Scales for Exploratory Outcome Sleep Quality Measures (CSHQ and ESS-CHAD)	35

LIST OF ABBREVIATIONS

ABC	Aberrant Behavior Checklist
ABC-H	Aberrant Behavior Checklist Hyperactivity Subscale
ADHD	Attention-Deficit/Hyperactivity Disorder
AE	Adverse Event
ALCOA-C	Attributable, Legible, Contemporaneous, Original, Accurate, Complete
ALT	Alanine Transaminase
AR	Aortic Regurgitation
ASD	Autism Spectrum Disorder
asQ	Ask Suicide-Screening Questions
AST	Aspartate Transaminase
AUC	Area Under the Concentration Time Curve
AUC _{ss/F}	Apparent AUC Versus Time Curve at Steady State
BID	Twice Daily
BMI	Body Mass Index
BMP	Basic Metabolic Panel
BP	Blood Pressure
BPCA	Best Pharmaceuticals for Children Act
BUN	Blood Urea Nitrogen
CBC	Complete Blood Count
CFR	Code of Federal Regulations
CGI-I	Clinical Global Impression Improvement
CGI-S	Clinical Global Impression Severity
CL _{ss/F}	Apparent Clearance
C _{max,ss}	Steady State Peak Drug Concentration
C _{min,ss}	Minimum Concentration
CMSU	Clinical Materials Services Unit
CNS	Central Nervous System
Coc	Certificate of Confidentiality
CPAP	Continuous Positive Airway Pressure
CSHQ	Child's Sleep Habits Questionnaire
DASH	NICHD's Data and Specimen Hub
DCC	Data Coordinating Center
DCRI	Duke Clinical Research Institute
DSMB	Data Safety Monitoring Board
DS	Down Syndrome
DUHS	Duke University Health System
eCRF	Electronic Case Report Form
ECG	Electrocardiogram
EDC	Electronic Data Capture e.g., Emmes Advantage eClinical®
ePRO	Electronic Participant Reported Outcomes
ER	Exposure-Response
ESI	Event of Special Interest
ESS-CHAD	Epworth Sleepiness Scale for Children and Adolescents
FDA	Food and Drug Administration
FWA	Federal-Wide Assurance

GCP	Good Clinical Practice
GER	Guanfacine Extended Release
GIR	Guanfacine Immediate Release
GMP	Good Manufacturing Practice
HCl	Hydrochloride
HDPE	High Density Polyethylene
HIPAA	Health Insurance Portability and Accountability Act
HR	Heart rate
ICF	Informed Consent Form
ICH	International Council for Harmonisation
ICMJE	International Committee of Medical Journal Editors
ID	Identification
IDD	Intellectual or Developmental Disability
IEC	Independent or Institutional Ethics Committee
IND	Investigational New Drug Application
IRB	Institutional Review Board
ITT	Intent to Treat
Kg	Kilogram
LAR	Legally Authorized Representative
LFT	Liver Function Tests
MedDRA®	Medical Dictionary for Regulatory Activities
Mg	Milligram
mL	Milliliter
MM	Medical Monitor
MOP	Manual of Procedures
NIH	National Institutes of Health
NICHD	National Institute of Child Health and Human Development
OAHI	Obstructive Apnea Hypopnea Index
PHI	Protected Health Information
PI	Principal Investigator
PK	Pharmacokinetics
PO#	Masked Packaging Code
PP	Polypropylene
PTN	Pediatric Trials Network
q.h.s	Every night at bedtime
REB	Research Ethics Board
SAE	Serious Adverse Event
SAR	Suspected Adverse Reaction
SD	Standard Deviation
SE	Standard Error
SOC	Standard of Care
SUSAR	Suspected, Unexpected, Serious Adverse Reaction
T _{max,ss}	Time at Peak Concentration
TORO	Transfer of Regulatory Obligations
TSH	Thyroid Stimulating Hormone
t _{1/2}	Half-life
UIP	University of Iowa Pharmaceuticals

ULN	Upper Limit of Normal
USP/NF	United States Pharmacopeia and National Formulary
V/F	Volume of Distribution
WBC	White Blood Cell
WGS	Whole Genome Sequencing

PROTOCOL HISTORY OF CHANGES

Version	Date	Summary of Changes
v1.0	27FEB2023	N/A Original protocol
v2.0	23MAY2023	
HR and BP assessment were added prior to each dose escalation.
 
Updated study design to indicate that participants will be given a FDA cleared device for parent/legal guardian to measure HR and BP remotely.
 
Added definition of HR and BP criteria that would prevent dose escalation.
 
Decreased HR and decreased BP were added as risks of Guanfacine Hydrochloride.
 
HR and BP criteria were initially listed as ESIs to only be assessed at in-person visits (Week 4 and Week 8). They have now been moved to the general list of Safety ESIs.
 
References and Table of Contents (TOC) were updated accordingly.

v3.0	29AUG2023	
Added IND Number
 
Updated number of sites to approximately 17 sites.
 
Updated Exclusion Criteria to include any changes to another medication used to treat symptoms of hyperactivity, inattention and impulsivity within 2 weeks.
 
Updated to indicate that the HR/BP device would be distributed at Day 1 (randomization) instead of at Screening.
 
Added clarification that parents would need to complete the Study Diary during the bridge/taper period for those who are in the GIR arm.

		
Updated definition of asQ from Ask-Suicidal-Screening Questions to Ask Suicide-Screening Questions.
 
Updated to indicate contraception is allowed but not required.
 
Specific references to pharmacy or pharmacist were removed and kept vague as site or clarified as pharmacist (or designee).
 
Changed concomitant medications to concomitant medications of interest.
 
Changed Study Product Diary to Study Diary since HR/BP was added to it.
 
Updated the definition of the efficacy population.
 
References and TOC were updated accordingly.

--	--	---

[figure not shown]
PROTOCOL SYNOPSIS

Protocol Title:	Guanfacine for Hyperactivity in Children with Down Syndrome (HYPEbeGONE_DS)
NCT #:	06042257
Phase:	Phase 2
Study Product(s) or Intervention:	Guanfacine hydrochloride, Immediate Release
Objectives:	
Primary:
 
1. Determine efficacy of guanfacine immediate release (GIR) for the treatment of hyperactivity/impulsivity and inattention in children with Down syndrome (DS) after 8 weeks of treatment. 
Secondary:
 
1. Characterize the safety profile of GIR in children with DS. 
Exploratory:
 
1. Characterize GIR exposure in children with DS.2. Characterize the exposure-response relationship of GIR for the treatment of hyperactivity/impulsivity, inattention, and sleep quality in children with DS.
Study Design:	Prospective, multi-center, randomized, double-masked, placebo-controlled, flexibly-dosed trial
Study Population:	Children ages 6-12 years old with DS
Inclusion Criteria:	
1. Parent/Legal Guardian can understand the consent process and is willing to provide informed consent/HIPAA authorization prior to the conduct of any study related procedures. When applicable, the minor participant is willing to provide assent.2. Participant has clinical diagnosis of non-mosaic DS.3. Participant is between 6 and 12 years of age (inclusive) at time of consent.4. Participant weight is ≥ 25 kg.5. Participant has clinically significant symptoms of hyperactivity, inattention and impulsivity manifested as minimum scores on both of the following rating scales within 30 days of randomization:
a. A minimum score of 18 on the parent-reported Aberrant Behavior Checklist - Hyperactivity (ABC-H) subscale, ANDb. A minimum score of moderate or greater (≥ 4) on the clinician-reported Clinical Global Impression Severity

	
(CGI-S) score specific to hyperactivity, inattention, and impulsivity behaviors.
 
6. Participant has co-morbid medical screening and clearance to proceed with a non-stimulant medication trial with GIR within 30 days of randomization.
 
7. Participant is willing and able to comply with study procedures, including adherence to medication dosing schedule.

Exclusion Criteria:	
1. Participant has received guanfacine (any formulation) within 30 days of randomization.
 
2. Participant has received any of the following concomitant medication classes within 30 days of randomization:
 
a. Strong CYP3A4 inhibitors (e.g., boceprevir, clarithromycin, conivaptan, grapefruit juice, indinavir, itraconazole, ketoconazole, lopinavir/ritonavir, mibefradil, nefazodone, nelfinavir, posaconazole, ritonavir, saquinavir, telaprevir, telithromycin, and voriconazole)b. Strong CYP3A4 inducers (e.g., avasimibe, carbamazepine, phenytoin, rifampin, and St. John's wort) 
3. Participant has a psychiatric comorbidity, such as major depressive disorder, bipolar disorder, obsessive-compulsive disorder, or a psychotic disorder, that requires a pharmacological treatment other than guanfacine.
 
4. For participants ≥ 8 years old at the time of consent, participant has a history of suicidality or positive screen on Ask Suicide-Screening Questions (asQ) Tool.
 
5. Participant is currently in or plans to participate in another interventional study.
 
6. Participant has a known hypersensitivity to guanfacine.
 
7. Participant has had a previous guanfacine treatment failure, as determined by their primary treating physician.
 
8. Participant has had a change in another medication intended to treat symptoms of hyperactivity, inattention, and impulsivity within the last 2 weeks.
 
9. Participant has had a seizure within the last 6 months.
 
10. Participant has had a change in their anti-convulsant dose within the last 4 weeks.
 
11. Participant has a cardiac-related condition including:
 
a. Significant symptomatic bradycardia;b. 2nd degree or 3rd degree (complete) heart block;

2 BACKGROUND INFORMATION AND SCIENTIFIC RATIONALE

2.1 Background Information

Section 409I of the Public Health Service Act, also known as The Best Pharmaceuticals for Children Act (BPCA) mandates the National Institutes of Health (NIH) to prioritize therapeutic areas in critical need for pediatric labeling; to sponsor pediatric clinical trials; and to submit these data to the Food and Drug Administration (FDA) for consideration for labeling changes. This study will be conducted in accordance with Section 409I of the Public Health Service Act; as such, the results from this research may be submitted to the FDA for review and use in negotiated labeling changes. This research study is contractually supported by the Eunice Kennedy Shriver National Institute of Child Health and Human Development (NICHD). The NICHD awarded a contract to Duke University (Durham, NC), which established a Pediatric Trials Network (PTN) through its Duke Clinical Research Institute (DCRI) to facilitate trial design for studies supported by the NIH. The NICHD awarded a separate contract to The Emmes Company, LLC (Rockville, MD) to serve as the Data Coordinating Center (DCC).

See ICH E6 (R2) GCP, Section 6.2

https://database.ich.org/sites/default/files/E6_R2_Addendum.pdf

2.1.1 Background of Attention-Deficit/Hyperactivity Disorder (ADHD) in Down Syndrome (DS)

Clinical significance of ADHD in patients with Down syndrome: Down syndrome (DS), caused by full or partial trisomy of chromosome 21, is the most frequent genetic cause of intellectual disability, occurring at an estimated prevalence of 12.9 per 10,000 individuals in the United States.^{1,2} Children with DS are at risk for many comorbid conditions that require chronic medication therapies, and very little is known about drug disposition and effect in this population specifically.

Psychiatric and behavioral disorders are common in children with DS, with estimates of psychiatric comorbidity up to 38%.³ Behavioral challenges, including hyperactivity and impulsivity, emerge as early as age 3, and it is estimated that between 10-45% of individuals with DS may be diagnosed with co-occurring ADHD^{4,5} putting this population at high risk for other disruptive behaviors and comorbidities.^{3,6-8} Hyperactivity and impulsivity place children with DS with baseline cognitive deficits at especially high risk for accidental injury and becoming lost or running away; and this becomes increasingly difficult to manage as they age into adulthood and other psychiatric comorbidities emerge.³ Furthermore, there is a growing body of evidence suggesting that the diagnosis of DS itself confers a specific risk for ADHD compared to the general population, even more than other conditions associated with intellectual disability.^{7,9}

Outcome measures for ADHD in DS: Identifying measures to evaluate cognition and behavior in children with intellectual or developmental disability (IDD) and DS specifically, within clinical trials has traditionally been challenging.¹⁰ Leading clinician and scientific experts were assembled by the NIH to review existing measures and identify those that are appropriate for clinical trials in individuals with IDD and specifically DS.¹¹ The Aberrant Behavior Checklist (ABC) is a rating scale that measures the severity of a range of problem behaviors commonly observed in individuals with IDD.¹² It is an empirically developed scale designed to measure psychiatric symptoms and behavioral disturbance exhibited by individuals with IDD across 5 domains: Irritability, Agitation, & Crying; Lethargy/Social Withdrawal; Stereotypic Behavior;

Hyperactivity/Noncompliance; and Inappropriate Speech, and it has been used extensively in pediatric and adult behavioral and psychiatric studies due to its high reliability and validity.^{11,13} The ABC-hyperactivity (ABC-H) subscale has been the primary outcome measure in the only trial of Guanfacine Immediate Release (GIR) for ADHD and disruptive behaviors in children with DS, as well as in several trials of ADHD with and without Autism Spectrum Disorder (ASD) in children.¹⁴⁻¹⁷ In addition to the ABC, the Clinical Global Impression (CGI) Scale will be utilized. The CGI was developed for use in National Institute of Mental Health-sponsored clinical trials to provide a brief, stand-alone clinician-determined summary measure prior to and after initiating a study medication that takes into account all available information, including a knowledge of the patient's history, psychosocial circumstances, symptoms, behavior, and the impact of the symptoms on the patient's ability to function.¹⁸ The CGI has two components – the CGI-Severity (CGI-S), which rates illness severity, and the CGI-Improvement (CGI-I), which rates change from the initiation (baseline) of treatment. The CGI is a widely used tool deemed appropriate for use in DS as identified by expert review. Previous studies have shown good concordance between parent/legal guardian and teacher ratings in neurotypical children¹⁹ and children with ASD,²⁰ which supports the utility of this measure as a behavior outcome measurement in children with DS.

Therapeutic options for treatment of ADHD in DS: Recommended management of ADHD in neurotypically developing children, depending on age, includes a combination of medications and behavioral therapy in young children and medications alone in school age children and older. Medications approved by the FDA to treat ADHD in children include stimulants and non-stimulant classes of medications.²¹ While stimulant medications (ex, methylphenidate, dextroamphetamine, amphetamines) are very effective in the treatment of ADHD in neurotypically developing children, and are in fact considered the preferred first line therapy, studies in neurodevelopmental disorders, such as ASD, suggest that individuals with neurodevelopmental disorders respond differently to stimulant medications. Not only have they been shown to be less effective, but also have decreased tolerability and an unacceptable side effect profile specifically upon appetite and growth.^{16,21} Furthermore, individuals with DS have an increased risk of congenital heart disease, which further limits the use of stimulant medications in this population.

Non-stimulant medications used for the treatment of ADHD include atomoxetine, clonidine, and guanfacine. Both clonidine and guanfacine are central alpha 2A-adrenergic receptor agonists thought to exert their actions through presynaptic stimulation and likely involve facilitation of both dopamine and noradrenaline neurotransmission, important in the pathophysiology of ADHD.²² Although the effect size is reportedly slightly less than the stimulant medications, non-stimulant medications are well accepted and may be preferred when stimulant medications are ineffective or the side effects intolerable, which has been reported in up to 30-50% of children and adults.²³⁻²⁵ Many thought leaders prefer guanfacine to clonidine in clinical practice because guanfacine has less sedation side effects than clonidine. Guanfacine IR (immediate release), or GIR, and Guanfacine Extended Release (GER) have been shown to be safe and effective in children with ASD and IDD,^{14,15,17} and one study has shown that GIR is effective and well tolerated in children with DS.⁶ However, only the extended release formulation, GER, is currently FDA approved for the treatment of ADHD as monotherapy and as adjunctive therapy to stimulant medications in children based on two clinical trials conducted in patients aged 6–17 years who met DSM-IV® criteria for ADHD.²⁶⁻²⁸

Prescribing guidelines report differences in pharmacokinetics and exposure between GIR and GER, and note that a dose substitution on a milligram for milligram basis will result in differences in exposure (INTUNIV® label).²⁶ GIR is 80% bioavailable and the relative bioavailability of GER tablets to GIR tablets is 58%. Compared to GIR, the Area Under the

Curve (AUC) and maximum serum concentration (Cmax) of GER tablets are 43% and 60% lower, respectively. Peak plasma concentrations occur 1 to 4 (average 2.6) hours after a single oral dose of GIR in adults and adolescents with hypertension and 5 hours after oral administration of extended-release tablets to children and adolescents with ADHD. However, studies have found that similar pharmacokinetics can be achieved between formulations. For example, plasma trough concentrations were similar in adults treated for smoking cessation with 3 mg/day administered BID of GIR and 4 mg/day of GER (3 mg/day GIR: M=3.40 ng/mL, standard error (SE) 0.34 vs. 4 mg/day GER: M=3.46 ng/mL, SE=0.67) with similar safety profiles between formulations.²⁹

The GER formulation is a practical challenge to prescribe in children with DS because the pill cannot be crushed and must be swallowed whole, and children with DS are at a high risk for comorbid dysphagia and swallowing dysfunction that puts them at significant risk for aspiration.³⁰ Safely swallowing tablets is a challenge. Children with DS have also been shown to have high risk for sleep apnea and baseline diminished blood pressure profiles compared to age-matched controls,³¹ thus this elevates the safety concerns for sedation and hypotension as known side effects that could be prolonged with an extended release formulation. As such, providers are using GIR to treat ADHD in children with DS in clinical practice with dosing strategies guided by the monitoring of side effects as doses are escalated. No formal dosing guidance exists for this population.

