2.1.2 Pediatric Labeling of Guanfacine

Adult: Guanfacine immediate release (GIR) is FDA approved for the management of hypertension. It may be given alone or in combination with other antihypertensive agents, especially thiazide-type diuretics.

Pediatric: Included on the GIR label: Safety and effectiveness in children under 12 years of age have not been demonstrated. There is no specific information included regarding the use for ADHD/hyperactivity, inattention, or impulsivity. Adverse reactions noted with guanfacine hydrochloride are similar to those of other drugs of the central α 2-adrenoreceptor agonist class: dry mouth, sedation (somnolence), weakness (asthenia), dizziness, constipation, and impotence. While the reactions are common, most are mild and tend to disappear on continued dosing. Adverse events (AEs) reported in post marketing at an incidence greater than 1% included dry mouth, dizziness, somnolence, fatigue, headache, and nausea.³²

There have been spontaneous post-marketing reports of mania and aggressive behavioral changes in pediatric patients with ADHD receiving GIR tablets. The reported cases were from a single center. All patients had medical or family risk factors for bipolar disorder. All patients recovered upon discontinuation of guanfacine tablets. Hallucinations have been reported in pediatric patients receiving guanfacine tablets for treatment of ADHD.

Included in the label for GER: INTUNIV® is indicated for the treatment of ADHD as monotherapy and as adjunctive therapy to stimulant medications. INTUNIV® was studied for the treatment of ADHD in three controlled monotherapy clinical trials (up to 8 weeks in duration) and one controlled adjunctive trial with psychostimulants (8 weeks in duration) in children and adolescents ages 6-17 who met DSM-IV® criteria for ADHD. The effectiveness of INTUNIV® for longer-term use (more than 8 weeks) has not been systematically evaluated in controlled trials.

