5.2 Inclusion/Exclusion Criteria

Inclusion Criteria	
1. Parent/Legal Guardian can understand the consent process and is willing to provide informed consent/HIPAA authorization prior to the conduct of any study-related procedures. When applicable, the minor participant is willing to provide assent.2. Participant has clinical diagnosis of non-mosaic DS.3. Participant is between 6 and 12 years of age (inclusive) at time of consent.4. Participant weight is ≥ 25 kg.5. Participant has clinically significant symptoms of hyperactivity, inattention and impulsivity manifested as minimum scores of the following rating scales within 30 days of randomization:
a. A minimum score of 18 on the parent-reported ABC-H subscale, ANDb. A minimum score of moderate or greater (≥ 4) on the clinician reported Clinical Global Impression Severity (CGI-S) score specific to hyperactivity, inattention and impulsivity behaviors.6. Participant has co-morbid medical screening and clearance to proceed with a non-stimulant medication trial with GIR within 30 days of randomization.7. Participant is willing and able to comply with study procedures, including adherence to medication dosing schedule.
Exclusion Criteria	
1. Participant has received guanfacine (any formulation) within 30 days of randomization.2. Participant has received any of the following concomitant medication classes within 30 days of randomization:
a. Strong CYP3A4 inhibitors (e.g., boceprevir, clarithromycin, conivaptan, grapefruit juice, indinavir, itraconazole, ketoconazole, lopinavir/ritonavir, mibepradil, nefazodone, nelfinavir, posaconazole, ritonavir, saquinavir, telaprevir, telithromycin, and voriconazole)b. Strong CYP3A4 inducers (e.g., avasimibe, carbamazepine, phenytoin, rifampin, and St. John's wort)3. Participant has a psychiatric comorbidity, such as major depressive disorder, bipolar disorder, obsessive-compulsive disorder, or a psychotic disorder, that requires a pharmacological treatment other than guanfacine.

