	
4. For participants \geq 8 years old at the time of consent, participant has a history of suicidality or positive screen on Ask Suicide-Screening Questions (asQ) Tool.5. Participant is currently in or plans to participate in another interventional study.6. Participant has a known hypersensitivity to guanfacine.7. Participant has had a previous guanfacine treatment failure, as determined by their primary treating physician.8. Participant has had a change in another medication intended to treat symptoms of hyperactivity, inattention, and impulsivity within the last 2 weeks.9. Participant has had a seizure within the last 6 months.10. Participant has had a change in their anti-convulsant dose within the last 4 weeks.11. Participant has a cardiac-related condition including:
a. Significant symptomatic bradycardia;b. 2nd degree or 3rd degree (complete) heart block;c. Baseline heart rate (HR) or systolic blood pressure (BP) $>$ 2 standard deviations (SD) below mean for age as determined by medical examination;d. History of aborted sudden cardiac death, unexplained syncope or near syncope, or historical use of a pacemaker as determined by medical history will require clearance by cardiology prior to enrollment;e. Known history of congenital heart disease which requires ongoing care for monitoring or management will require clearance by cardiology prior to enrollment.12. Participant has a history of untreated severe obstructive sleep apnea defined as obstructive apnea hypopnea index (OAHI) \geq 10 events per hour or aortic regurgitation (AR). Participants with an OAHI index $>$ 10/hr are eligible if managed with continuous positive airway pressure (CPAP).13. Participant has untreated thyroid disease.14. Participant has a known hepatic impairment defined as aspartate aminotransferase (AST) or alanine aminotransferase (ALT) $>$ 2x the upper limit of normal (ULN) for age.15. Participant has known impending or renal failure defined as:
a. Anuria diagnosed within 12 hours prior to enrollment;b. Requiring renal replacement therapy.16. Participant is pregnant (refer to Section 7.6.1).17. Participant has any condition which would make the participant, in the opinion of the investigator, unsuitable for the study.
--	---

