6.17 Concomitant Medications of Interest/Treatments

Concomitant medications of interest include the following: central nervous system (CNS) depressants (example: benzodiazepines, barbiturates, opioids), anti convulsants (example: carbamazepine), CNS stimulants or non-stimulants to treat ADHD (e.g., methylphenidate, dextroamphetamine, amphetamines, clonidine, atomoxetine, bupropion) and antibiotics (e.g., ciprofloxacin, clarithromycin, erythromycin, fluconazole, itraconazole, voriconazole, rifampin).

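### Nothing bars starting clonidine or another alpha-2 agonist during the 8 masked weeks, and antihypertensives and beta-blockers are not on the recorded drug list

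*Combined protocol and SAP*

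**What the plan says.** **Drug class.** Section 2.1.1 places the two drugs together: "Both clonidine and guanfacine are central alpha 2A-adrenergic receptor agonists thought to exert their actions through presynaptic stimulation". It reports as a reason for preferring guanfacine that "guanfacine has less sedation side effects than clonidine". The add-on pediatric trial mentioned in 2.1.2 (GER label) is "one controlled adjunctive trial with psychostimulants (8 weeks in duration"); none is cited with a second alpha-2 agonist.

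**Entry rules (5.2).** Exclusion 1: "Participant has received guanfacine (any formulation) within 30 days of randomization". Exclusion 7: "Participant has had a previous guanfacine treatment failure, as determined by their primary treating physician". Exclusion 2 covers strong CYP3A4 inhibitors and inducers only. For other ADHD drugs the rule is exclusion 8: "Participant has had a change in another medication intended to treat symptoms of hyperactivity, inattention, and impulsivity within the last 2 weeks". Clonidine appears in no exclusion.

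**On-study drugs (6.17).** This section lists concomitant medications of interest. They include "CNS stimulants or non-stimulants to treat ADHD (e.g., methylphenidate, dextroamphetamine, amphetamines, clonidine, atomoxetine, bupropion"). The section prohibits nothing. Table 1 collects these medications at Screening, Week 4 and Week 8, and a note in 6.7.1 limits the eCRF to drugs on this list. Neither antihypertensives nor beta-blockers appear as a class.

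**Analysis (10.4.1).** Use of alternative ADHD agents is one of several covariates that may be examined in additional analyses. The section does not say how a drug started after randomization is handled. The per-protocol definition in 10.3.2 considers compliance and correct treatment only.

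**The concern.** The protocol is careful about prior guanfacine but has no specific rule for a drug that it puts in the same class and describes as more sedating. Two consequences matter.

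First, exclusion 8 controls changes only before randomization. A drug started afterwards is not part of the baseline score, and randomization does not balance it, because the decision to start can depend on how the child is doing. If children not improving on placebo are more likely to be given clonidine, the placebo mean at Week 8 improves for a reason other than placebo and the treatment difference shrinks. In the GIR arm, a start would put a second drug of the class on top of an escalating dose. Decreased heart rate and blood pressure are listed guanfacine risks (2.4.2), and 2.1.1 describes lower baseline blood pressure in children with Down syndrome.

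Second, hypotension and bradycardia are solicited safety events (7.1.2), and exclusion 11e lets in children with managed congenital heart disease after cardiology clearance. Some of these children may plausibly take drugs that lower heart rate or blood pressure, yet the trial dataset would not show it.

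**Working it through.** **1. Does any rule reach clonidine?**
- Stable at entry: exclusions 1 and 7 name guanfacine only, exclusion 2 is limited to CYP3A4 drugs, and exclusion 8 requires a recent change. Stable clonidine passes.
- Started on study: 5.2 applies at entry, 6.17 is a recording list, and the hold, split and reduce rules in 6.13.1 concern study product. No rule applies.

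**2. Is clonidine recorded?** Yes, by name in 6.17. The recording gap therefore concerns antihypertensives and beta-blockers, not clonidine.

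**3. The plan's own power figure (10.6).** d = (26 − 20.6)/6 = 0.90. At 2:1, 48 evaluable children are 32 and 16. The noncentrality is 0.90 × √(32 × 16/48) = 2.94 on 46 degrees of freedom. Two-sided power at 0.05 is 82.1%, and 48/(1 − 0.20) = 60. The plan's figures reproduce.

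**4. Stable clonidine at entry (share f assumed; the documents give none).** Of 60 randomized, 40 receive GIR. The expected number on both drugs is 40f, and the chance of at least one is 1 − (1 − f)^40.

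| f | Expected | At least one |
|---|---|---|
| 1% | 0.4 | 33% |
| 2% | 0.8 | 55% |
| 5% | 2 | 87% |
| 10% | 4 | 99% |

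These figures measure exposure, not harm. If users keep a fraction r of the GIR effect, d = 0.90 × [1 − f(1 − r)]. At f = 5%, power is 78.0% (r = 0), 80.1% (r = 0.5) or 82.1% (r = 1). At f = 10% it is 73.6%, 78.0% or 82.1%.

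**5. Starts after randomization, in the unfavourable pattern.** Suppose a share g of placebo children start such a drug, each gains a fraction k of the planned 5.4-point difference, nobody starts in the GIR arm, and the SD stays at 6. Then d = 0.90 × (1 − gk).
- g = 5%, k = 1: d = 0.855, power 78.0% (16 × 0.05 = 0.8 of a child).
- g = 10%, k = 0.5: d = 0.855, power 78.0%.
- g = 10%, k = 1: d = 0.81, power 73.6% (1.6 children).

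If starts were equally common in both arms and helped equally, the expected difference would not change. Both g and k are assumptions.

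**The case against.** A reader might infer that letting in children on stable clonidine is an error, that it biases the comparison, or that the combination is shown to be unsafe. The documents support none of these.

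- Exclusion 8, the 6.17 list and the optional covariate in 10.4.1 fit together as one policy: background ADHD drugs may continue if stable, are recorded, and can be examined. The change history shows that the stability rule was added at version 3.0. The 6.17 list also names "antibiotics (e.g., ciprofloxacin, clarithromycin, erythromycin, fluconazole, itraconazole, voriconazole, rifampin"), some of which exclusion 2 bars. That does not undercut the policy, because exclusion 2 covers only the 30 days before randomization and later use still needs recording.
- Stable clonidine is already reflected in the baseline ABC-H score and is balanced between arms in expectation.
- No passage calls the combination unsafe. Additive sedation, hypotension or bradycardia is an inference from the shared class.
- Risk is managed: medical clearance (inclusion 6), the low heart rate or systolic pressure exclusion (11c), investigator discretion (17), home readings before each escalation (6.8), and dose holding, splitting or reduction (6.13.1).
- The remark in 4.9 about adding an agent when 3 mg is not enough explains the dose cap from clinical practice. It does not show that drugs will be added on study.

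All of this stands, and it removes any case for calling entry on stable clonidine a defect. It does not close the two gaps. The stability rule stops at randomization, and the optional covariate cannot cleanly repair a start that is itself a response to how the child is doing. On recording, screening history and source records would allow some retrieval, but only piecemeal and outside the dataset. The Manual of Procedures is not among the documents and might contain a rule. If so, the protocol should state it.

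**Conclusion.** A modest point on safety and interpretability, worth considering. Admitting stable clonidine is a defensible choice; excluding it as same-class duplication would be defensible too, as a trade-off against recruitment.

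What holds is narrower: no on-study limit on starting clonidine or another alpha-2 agonist, and no recording of antihypertensives or beta-blockers. For the first, any blurring of the primary result would be towards a smaller difference if starts concentrate in placebo children. Under the assumptions shown, one or two such children could cost about 4 to 8 points of power. For the second, the comparison of event rates between arms remains protected by randomization, and a clinician judges causality for each event. What is lost is the ability to read, or adjust, individual hypotension and bradycardia events against these drugs. No power or sample size figure in the plan needs to change.

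**What to change.** In 6.17:

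1. State that clonidine and other alpha-2 agonists should not be started during the 8-week masked period, and that any start is recorded with its date.
2. Add drugs that lower heart rate or blood pressure (for example antihypertensives and beta-blockers) to the recorded list.

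The cost is one more recorded drug class and a minor limit on co-prescribing for 8 weeks. Both must be in place while data are collected, since the analysis cannot supply them afterwards.

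Optionally, the sponsor could widen exclusion 1 to all alpha-2 agonists. At an assumed 5% share, 60/(1 − 0.05) ≈ 63 otherwise eligible children would be needed to randomize 60. Families should not be asked to stop clonidine in order to enrol. If the sponsor prefers to keep stable clonidine, one sentence in 5.2 or 6.17 saying so would give the sites a common rule.
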